## **2.6 Rationale**

We propose the use of a multi-arm, phase II “pick-the-winner” trial design to allow initial assessment of multiple therapies in parallel and selection of promising therapies with adequate probabilities after COVID19 + testing in high risk, but non-critically ill individuals. [47] Prior to moving a promising therapeutic agent forward into large randomized trials of this therapy versus placebo, investigators need to provide substantial evidence of effectiveness and adequate characterization of safety. In addition, we incorporate rapid futility analysis where each agent is assessed independently using Bayesian posterior probability calculations. **NOTE: this is based on efficacy not toxicity assessment. The toxicity assessment will be done using run-ins for some of the arms.** This selection design approach along with interim assessments of efficacy,, used often in other disciplines such as oncology, allows for initial assessment of potential benefit using statistical probability calculations, before designing randomized comparative trials to avoid exposing large numbers of subjects to potentially futile agents. The “pick the winner” trial design and Bayesian posterior probability methods allow for an adaptive, proof-of-concept strategy which incorporates prospectively planned criteria to stop each arm independently for futility,[48] [49] with the prospect of expanding from a proof-of-concept phase to a larger confirmatory trial, typically a randomized, placebo controlled trial, if initial assessments are positive. The hypothesis of this study is that the addition of agents that inhibit viral entry or replication of SARS-CoV-2 virus, will be devoid of additional moderate to severe toxicities, will prevent clinical deterioration at 14 days, and will improve viral clearance at Day 14 in high risk individuals. Additionally, we hypothesize that clinical outcomes in COVID-19 infected patients at higher risk of poor outcomes following infection will be improved compared to the emerging standards when introduced as an early intervention after diagnosis.

COVID 7-point Ordinal Outcome Scale and Primary Endpoint

## 2.7 Correlative Studies Background

### 2.7.1 SARS-CoV-2 Viral Load

Active SARS-CoV-2 infection is diagnosed by qPCR in upper and lower respiratory specimens obtained by nasopharyngeal swabs. The initial, diagnostic test is performed at baseline in a CLIA laboratory and required for diagnostic purposes and for study entry. Subsequent samples, to avoid placing burden on clinical resources, will be research level oropharyngeal swabs or sputum samples and evaluated in the [name] laboratory by a validated qPCR assay. In addition, any residual specimen from nasopharyngeal swabs that are collected for routine care due to a clinical indication to retest using a CLIA laboratory assay will be collected. Correlative testing will examine the linkage of viral load with time to resolution and with clinical status, as well as correlation between viral load and seropositivity, recrudescence, of disease and clinical outcomes.

### 2.7.2 SARS-CoV-2 Antibody Seropositivity

Definitive methods to prove a patient had been infected with SARS-CoV-2 are currently lacking. Several groups within the UK system are developing serology tests to detect SARS-CoV-2 antibodies. [name], an Associate Professor in Engineering at the University of Kentucky and Chief Scientific Officer of Salas Discovery, is an expert the development of point of care testing for viral diagnostics. He has adapted an emerging technology in biomarker isolation/measurement, Exclusion-based Sample Preparation (ESP), for the unmet clinical need associated with point of care SARS-CoV-2 measurement. [50] This serology test combines the sensitivity and quantitative nature of an ELISA with the speed and simplicity of a lateral flow assay (i.e., a rapid test) [51-53] Briefly, ESP utilizes phase interfaces (e.g., liquid/air boundaries) to rapidly and simply manipulate analyte bound to paramagnetic particles (PMPs) within a bulk sample. ESP will be used to isolate SARS-CoV-2 antibody from a blood sample and then perform a streamlined, ESP-based immunoassay for quantitation SARS-CoV-2 antibody. Importantly, ESP that has been successfully implemented as the backbone of a new HIV assay geared toward developing countries, illustrating its ability to function outside of sophisticated labs.[54, 55]

Members of the University of Kentucky CURE Alliance including [name] has expertise in development of immune profiling and in collaboration with other members of the

Department of Microbiology, Immunology, and Molecular Genetics and other collaborators is developing an in-house serological assay to test for the presence of antibodies to SARS-CoV-2 infection in blood and saliva which will be critical to our ability to understand immunity to this virus following infection. Additionally, his group will pursue complete immune profiling of plasma based mononuclear cells (PBMCs) which is an associated and critical part of expanding our understanding of the adaptive immune response to this novel virus.

### **2.7.3 Inflammatory Cytokines**

Prior studies have demonstrated that proinflammatory cytokines are associated with pulmonary infiltrates and severe infection in individuals with SARS, [56] MERS- CoV [57] and SARS-CoV-2 [2] infection. We hypothesize that inflammatory cytokines like TNF alpha, IL-1, IL-2 and IL-6 will be elevated at baseline and day 7 in individuals who go on to develop a severe infection when compared to those who do not develop a severe infection and that cytokine measurement can be an early marker of severe infection, allowing for earlier intervention in these individuals. Cytokine levels will be measured by the ELISA in the [name] lab, by [name], as previously described. [58]

### **2.7.4 Coagulopathy in COVID-19 Patients**

[name] (Molecular and Cellular Biochemistry) and [name] (Medicine) have developed a collaboration to study the coagulopathies associated with COVID-19 patients. Specifically, their focus is on the dysfunction of normal hemostatic control seen in the most severe COVID-19 patients. Reports from China, Italy, and the US have shown an increase in coagulopathies in COVID-19: presenting as increased D-dimer, thrombocytopenia, and thrombotic microangiopathy. This clinical manifestation has led ISTH and ASH to recommend low molecular weight heparin in cases where COVID-19 is severe; however, the underlying causes of this are unknown. Drs. [name] and [name] will use their specific expertise and battery of functional assays to study this coagulation dysfunction at both the coagulation factor and platelet level. Whole blood is needed for some of the platelet-specific assays and plasma will be retained for analysis. The data generated will help determine what causes the increased coagulation and will guide how to better manage anticoagulant therapy in the most severely affected patients.

## **3. PATIENT SELECTION**

### **3.1 Eligibility Criteria**

3.1.1 Age  $\geq$ 18 years

3.1.2 Laboratory-confirmed SARS-CoV-2 infection within 7 days (of proposed consent) or the presence of symptoms or physical examination signs providing high probability of COVID-19 disease despite a negative COVID-19 test as determined by Infectious Disease specialist/COVID-19 Telehealth Treatment Team review

3.1.3 Subjects must have at least one of the following high-risk features for clinical

deterioration:

- Hypertension
- Diabetes Mellitus
- Moderate to severe Chronic Obstructive Pulmonary Disease, Emphysema, Cystic Fibrosis, or Asthma
- Cancer patients who have received any immunosuppressive drugs within a year from enrollment.
- Sickle cell disease or thalassemia
- Age  $\geq 50$
- BMI  $\geq 30$
- Living in a nursing home or long-term facility
- Underlying serious heart condition as determined by the treating physician
- Immunocompromised subject as defined by the treating physician or COVID-19 Telehealth Treatment Team

3.1.4 Ability to provide informed consent by the patient or healthcare proxy

3.1.5 Ability to return for repeated testing and observation to UKHC

3.1.6 Patients must have adequate organ and marrow function measured within the last 30 days as defined below:

- platelets  $\geq 100,000/\text{mcL}$
  - AST(SGOT)/ALT(SGPT)  $\leq 3 \times$  institutional ULN
  - creatinine  $\leq 1.5 \times$  institutional ULN
- OR
- glomerular filtration rate (GFR)  $\geq 45 \text{ mL}/\text{min}/1.73 \text{ m}^2$  unless data exists supporting safe use at lower kidney function values, no lower than  $30 \text{ mL}/\text{min}/1.73 \text{ m}^2$  (see Appendix B).

3.1.7 The effects of therapeutic agents used in this trial on the developing human fetus are unknown. Because therapeutic agents used in this trial may be teratogenic, women of child-bearing potential and men must agree to use adequate contraception (hormonal or barrier method of birth control; abstinence) prior to study entry and for the duration of study participation. Should a woman become pregnant or suspect she is pregnant while she or her partner is participating in this study, she should inform her treating physician immediately. Men treated or enrolled on this protocol must also agree to use adequate contraception prior to the study, for the duration of study participation.

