#### 4.9 Patient Registration to Treatment

To register a patient, the following information should be reviewed by the clinical research nurse (CRN) / clinical research associate (CRA) with the study physician per MCC SOPs to confirm eligibility:

- Copy of COVID19 testing results
- Mobile EKG tracing (outpatients) or standard EKG (inpatients) within 5 days of registration to assess QTc interval
- Eligibility labs, as well as correlative labs to be drawn
- Eligibility Checklist

Once eligibility is confirmed, the CRN/CRA will complete subject registration in the OnCore database (minimum data footprint) for randomization and complete study-required RedCap data forms. To complete the registration process, the CRN/CRA will:

- assign a patient study number
- register the patient on the study in OnCore
- receive the automated treatment arm assignment
- send an email or other communication to the study team of arm assignments.

If a patient is deemed ineligible for treatment their specimens will be retained in the COVID19 BIOBANK if the subject has indicated agreement to specimen collection and long-term storage in the consent form.

At the Day 1 visit or inpatient the following will be completed

- 1) Sign **treatment informed consent** (unless previously e-consented as above)
- 2) Undergo blood testing for eligibility (in subjects who have not had assessment of screening labs within the last 30 days will require blood draw)
- 3) Complete an eligibility questionnaire (age, concurrent diseases, current medications, contact information)
- 4) Undergo a mobile EKG or standard EKG tracing to assess QTc interval (within 5 days of registration)
- 5) Distribute medications, pill diary, and instructions
- 6) Baseline correlative blood sample
- 7) Sputum sample, with OP swab (alternative, if no sputum available)
- 8) Saliva sample
- 9) COVID-19 ordinal scale assessment (See Appendix B)
- 10) Limited visual physical exam unless a more complete exam is clinically indicated.

Day 3 or 4 phone call to assess clinical status and elicit concerns or questions.

Day 7 telehealth (+/- 4 days) is required for all patients to assess toxicity. If a subject has a standard of care telehealth visit during this period, this is also an acceptable toxicity assessment.

Day 10 or 11 phone call to assess clinical status and elicit concerns or questions

Day 14 (+/- 4 days) visit will also be completed in clinic or inpatient hospital.

- 1) Undergo blood testing for toxicity

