Since there are no safety data for the medications to be evaluated on all arms of this study in the mild to moderate SARS-CoV-2 infected population, the first six patients on each arm will be evaluated for any grade 3 or higher hematologic or non-hematologic toxicity for 14 days. Patients coming off study before the first 14 days for reasons other than toxicity will be replaced. If two or more of the six patients in this arm of the study develop unacceptable toxicity, the treatment for that arm would be considered unsafe and stopped. Patients exhibiting rapid progression of COVID-19 symptomatology requiring intensive care hospitalization or intubation will come off study and will be considered failures in terms as per the primary endpoints of the study but nor for safety and will be replaced if these cases occurred during the phase 1 portion of the study.

Once the phase 1 portion safety run-in has concluded, that arm will be opened for phase II accrual.

Patients will be assigned to each arm in cohorts of three at a time until accrual numbers for each arm are fulfilled or discontinued due to safety concerns occurring beyond the Phase 1 portion. Monthly phone conferences among investigators during enrollment will take place.

Patients will undergo baseline mobile EKG or standard EKG to evaluate QTc interval on Day 1 (or within 5 days of registration if inpatient) and a repeat EKG at Day 14 (+/-4 days). Any Chest X-ray or CT scan of the chest that is performed for routine care will be reviewed by the PI for eligibility and recorded on case report forms. NOTE: if a patient develops a myocardial infarction or grade 3 or 4 cardiac arrhythmia while on the 14 days of drug, they should be immediately taken off study medication and receive standard of care treatment per their treating physician.

Patients will be followed for clinical outcomes by phone contact each week and hospitalizations, and all complications will be recorded on adverse event case report forms.

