## **6.2 Definition of Dose-Limiting Toxicity (DLT) for phase I run in portions of this protocol**

A DLT is defined as any of the below treatment emergent toxicities with attribution of definitely, probably or possibly related to one or more of the study drugs that occur during the first 14 days of study treatment. Toxicities that occur after the 14 day treatment period will be reported through adverse event reporting outlined in section 10.0, but will not be counted as DLTs.

- **Grade 3 or higher non-hematologic or non-hematologic toxicity at least possibly, probably or definitely related to study medication or procedures, per DMID Toxicity Scale for Determining Severity of Adverse Events**

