#### 9.4 Randomization/Stratification Factors

Blocked randomization with equal allocation will be utilized with adjustment in randomization sequence to account for the potential to drop an arm. Block size is 2 times the number of treatment arms. Randomization will be stratified by outpatient or inpatient status at time of enrollment into the trial.

Randomization lists will be generated prior to study enrollment and provided to the IDS pharmacist who will be in charge of the randomization with the randomization coordinator. All other study personnel including the PIs will be blinded to the randomization lists to prevent patient and investigator bias. Patients who are eligible for randomization will be assigned to a treatment arm according to the randomization list.

In the scenario where a treatment arm is terminated early or a new treatment is added into the study, a new randomization list may be generated to replace the existing one. The randomization list will give every patient equal probability to each study arm that is currently available.

The randomization list will be incorporated into the OnCore Clinical Trials Management System and accessible to the IDS pharmacist. This is facilitated by the OnCore CTMS which assigns different access and restriction levels depending on personnel role in the study. Treatment allocation for each patient is thus performed by the IDS pharmacist after Study Coordinator confirms patient eligibility status.

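### Section 3.1.6 says it defines adequate marrow function but limits only platelets, so grade 3-4 neutropenia or anemia at entry passes every written laboratory criterion, even though patients may be randomized to artesunate (Arm F)

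*Combined protocol and SAP*

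**What the plan says.** Section 3.1.6 opens with "Patients must have adequate organ and marrow function measured within the last 30 days as defined below". The items below it are platelets ≥100,000/mcL, AST/ALT ≤3 × ULN, and creatinine ≤1.5 × ULN or a GFR limit. The exclusions in 3.2 that involve measured organ function cover oxygenation (3.2.1), renal function (3.2.5) and hepatic failure of DMID grade 3 or worse (3.2.6). None is hematologic.

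Section 8.1.6 lists neutropenia, anemia and nausea for artesunate under toxicities above 10%, without grades. Section 7 (dose delays and modifications) reads N/A.

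On the order of events, 4.9 says "Once eligibility is confirmed, the CRN/CRA will complete subject registration", after which the system returns the arm. Section 9.4 adds: "The randomization list will give every patient equal probability to each study arm that is currently available".

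As safeguards, 4.9 has the study physician review several items before registration, among them "Eligibility labs, as well as correlative labs to be drawn", and 3.2.16 lets the treating physician exclude a patient for any other condition. Once dosing starts, 6.1 provides a run-in: "the first six patients on each arm will be evaluated for any grade 3 or higher hematologic or non-hematologic toxicity for 14 days". The arm stops on this condition: "If two or more of the six patients in this arm of the study develop unacceptable toxicity".

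**The concern.** The criterion does not define what it says it defines. The two counts it leaves out, neutrophils and hemoglobin, are the two that the protocol lists as commonly affected by artesunate. A site that checks a patient against 3.1.6 finds no line on which severe neutropenia or severe anemia would fail.

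Such patients are plausible in this population. Section 3.1.3 recruits people with sickle cell disease or thalassemia, cancer patients given immunosuppressive drugs within the past year, and other immunocompromised patients. The three-week break from antineoplastic treatment in 3.2.13 does not require a recovered count.

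The stake is patient safety. Someone already at grade 3 or 4 could start 14 days of an agent with these listed toxicities, with no written entry limit to prevent it.

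**Working it through.** The plan states no figure to reproduce. The check compares the written criteria with the toxicity scale and then follows the patient to Arm F.

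**1. Entry limits against the DMID grades in Appendix G**

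| Count | Grade 3 | Grade 4 | Limit in 3.1 or 3.2 |
|---|---|---|---|
| Platelets (/mm³) | 20,000-49,999 | <20,000 | ≥100,000, which excludes even grade 1 (75,000-99,999) |
| ANC (/mm³) | 500-749 | <500 | none |
| Hemoglobin (g/dL) | 6.5-7.9 | <6.5 | none |

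**2. Test patients.** The written rule of 3.1.6 is: platelets ≥100,000, and AST/ALT ≤3 × ULN, and (creatinine ≤1.5 × ULN or GFR ≥45). Take platelets 150,000, AST/ALT 1 × ULN, creatinine 1 × ULN and GFR 90, and vary one count at a time:

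- hemoglobin 7.9 (grade 3): passes
- hemoglobin 6.4 (grade 4): passes
- ANC 749 (grade 3): passes
- ANC 499 (grade 4): passes

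**3. Route to Arm F.** Eligibility is settled before assignment (4.9) and allocation is equal across open arms (9.4). With four arms open, each eligible patient has a 1/4 chance of Arm F.

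**4. Safeguards, by when they act**

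- *Before dosing:* discretion (3.2.16), lab review (4.9) and the antineoplastic break (3.2.13). None names an ANC or hemoglobin value.
- *After dosing starts:* the run-in, later safety stopping of an arm and weekly phone contact (6.1); contacts on Days 3/4, 7 and 10/11 (4.9); stopping an individual's treatment (6.3); hematologic safety endpoints (9.2); arm decisions that weigh safety (9.6); expedited reporting (10.3); and DSMC review (13.3). A DLT must be among "treatment emergent toxicities with attribution of definitely, probably or possibly related" to study drug (6.2), so a low count at baseline is not itself a DLT.

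**5. Sizes that follow from the documents**

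- Run-in share of Arm F: 6/60 = 10%, which leaves 60 − 6 = 54 patients outside the two-of-six rule.
- First scheduled CBC after Day 1: Day 14 ± 4, that is Day 10 to Day 18. Daily doses taken by then run from 9 (Day 10, before that day's dose) to 14 (Day 15 onward). Inpatients may have routine counts sooner.
- Anemia in the larger malaria trial cited in 2.5: 7/941 = 0.74%, pooled over three groups, one of which did not receive artesunate.

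**6. Illustration only.** The documents give no rate of grade 3-4 counts at entry. Assume a proportion r, with no source, before discretion or lab review removes anyone:

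| r | Arm F at full size, 60r | Arm F if stopped at the first look, 10r | Whole trial, 240r |
|---|---|---|---|
| 0% | 0 | 0 | 0 |
| 1% | 0.6 | 0.1 | 2.4 |
| 2% | 1.2 | 0.2 | 4.8 |
| 5% | 3.0 | 0.5 | 12 |

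These are counts of enrolments, not of harm.

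**The case against.** The strongest reply is that the risk is unquantified and probably small. The study physician sees the labs before registration and the treating physician may exclude anyone, so the scenario needs a clinician to see, say, an ANC below 500 and enroll anyway. The clinical data in 2.5 are mostly reassuring: 7 anemias in 941 patients, one severe anemia in another trial judged likely unrelated, and use of the same 200 mg daily dose for up to 37 months in cancer studies. The tight platelet floor proves no inconsistency either, because thrombocytopenia is listed for camostat.

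Much of this stands, and it limits what can be claimed. A reader might infer that artesunate is known to push such patients into danger. The documents do not support that: 8.1.6 gives neither grades nor the size of any fall. A reader might also take 6.1's statement that "there are no safety data for the medications to be evaluated on all arms of this study" as evidence of special hazard. In context it is the reason given for the run-in. Nor can one say that the plan has no protection, given the safeguards listed above.

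The reply does not close the gap. The review in 4.9 has no ANC or hemoglobin threshold to apply. The malaria trials enrolled mainly children, and no cited result is broken down by count at entry. The remaining safeguards act only once the patient has started treatment.

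A last objection is that floors for all arms go too far, because 3.2.11 already writes agent-specific exclusions and neither neutropenia nor anemia is listed for the other agents. That is fair: floors in every arm are a preference, not a necessity.

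**Conclusion.** The point holds as a gap in the eligibility rule and should be corrected. As written, a patient at DMID grade 3-4 on ANC or hemoglobin passes every laboratory criterion and may be assigned to Arm F, and only clinical judgment without a stated threshold stands in the way before dosing.

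This rests on the text of 3.1, 3.2, 4.9, 8.1.6, 9.4 and Appendix G, and needs no assumption about prevalence. The size of the risk does need one, and the documents do not supply it. The 0 to 3 Arm F entrants in the illustration follow from an assumed 0-5% and should not be read as an estimate. The conclusion is therefore that a safety criterion is incomplete. It is not that harm is expected or that many such patients would enroll.

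**What to change.** Add two lines to 3.1.6: ANC ≥750/mm³ and hemoglobin ≥8.0 g/dL. They exclude DMID grade 3 or worse at entry, in line with the hepatic exclusion in 3.2.6. For sickle cell disease or thalassemia, which 3.1.3 recruits on purpose, set a lower hemoglobin floor, for example ≥6.5 g/dL, so that only grade 4 is excluded. The cut-offs are a clinical choice and the investigators may adjust them.

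Preferably apply the floors to every patient before assignment while Arm F is open, so that no one is randomized to an arm they cannot take and the arms being ranked keep the same entry population. The alternative is to remove Arm F, before randomization, from the arms open to a patient below the floor. That keeps such patients in the trial but needs its own provision in the randomization list.

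No new blood draw is needed, because the CBC with differential is already in the Study Calendar. The cost is a few patients not enrolled. On the same unsourced range it is at most 2.4 of 240 for each 1% of patients with such counts (0 to 12 at 0-5%), and fewer with the lower hemoglobin floor.

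The change leaves two things as they are: labs up to 30 days old still count, and no CBC is scheduled between Day 1 and Day 10. Grade 2 counts would still be admitted.
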